**Specific Aim 3: Demonstrate a dose-response relationship between exercise intensity and chronic inflammation in HIV+ and HIV- adults aged 50 to 75 years.**

Hypothesis 3a: Older HIV+ adults will have a lower acute response to exercise (lower systemic IL-6 and TNF $\alpha$ ) at baseline and with 12 weeks training, in comparison to HIV- older adults.

Hypothesis 3b: Older HIV+ adults training on a high-intensity exercise regimen for 12 weeks will experience a greater initial increase in systemic IL-6 without a detrimental increase in TNF $\alpha$  in response to an acute bout of exercise, compared to those randomized to moderate-intensity exercise Hypothesis 3b: After 24 weeks of training, older HIV+ adults randomized to high-intensity exercise will experience a greater relative decline in chronic (resting) markers of systemic inflammation (IL-6, STNFRI, TNF $\alpha$ ) compared to those randomized to moderate-intensity exercise and compared to HIV- adults.

Specific Aim 4: Use qualitative methods to understand the barriers and facilitators to starting and maintaining an exercise program among older, HIV-infected population with multiple health disparities.

Hypothesis 1. Barriers to exercise will be identified among older HIV-infected men and women; these issues may focus around themes such as access to exercise facilities, body image, income/resources, stigma of HIV, and social support. Facilitators to routine physical activity and to continuation of exercise after completion of the exercise program will include greater exercise self-efficacy.

Methods: Focus group and individual interviews will be conducted among 1) participants who are currently exercising or who recently completed the exercise intervention study (K23 AG050260), or 2) participants not enrolled in the study. Participants will be men or women with HIV infection, aged 50 and older who are either exercising regularly or not exercising, similar to the recruitment criteria for the current participants. Semi-structured interviews for group interviews will be framed around the theoretical framework of behavior change, self-efficacy, and the Social Ecological Model.

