## C. Study Design and Research Methods

Potentially eligible subjects will be screened during routine clinic visits or over the telephone. Potentially eligible and interested subjects will return for informed consent and a screening/baseline visit. No research procedures will occur prior to consent, including the MOCA.

After obtaining informed consent, participants will undergo a graded exercise test to screen for potential underlying cardiovascular disease. V02 peak will be measured at this time to develop the exercise prescription. All participants will begin with a low intensity lead-in for 1-2 weeks, then advance to a moderate intensity exercise during first 12 weeks. Randomization to continue on moderate versus advance to high intensity will occur at week 13.

**1. Consent & baseline visit.** After obtaining consent, the participant will be evaluated

-After obtaining consent, the participant will be evaluated by

- medical history, physical examination including vital signs
- Montreal Cognitive Assessment (MOCA)
- Resting BP, 12-lead resting ECG, and then a graded exercise test (GXT) administered by research personnel and a clinician experienced in exercise stress testing of older adults ([name]) to screen out volunteers with evidence of ischemic heart disease, serious arrhythmias, or abnormal HR/BP responses to exercise. Briefly, the test will begin at a comfortable walking speed and 0% elevation; speed will be maintained and the grade increased by 2% every 2 min, until the participant reaches 85% of age-predicted maximal heart rate or the test is otherwise terminated. The absolute and relative indicators for terminating an exercise test that are recommended by the American College of Sports Medicine (ACSM) will be employed.
- Baseline physical function assessments will be administered.

**2. Procedure visit #1 (within 14 days of visit #1).** All participants will arrive between 7:30-8am for:

- DXA scan
- Vital signs
- Anthropometrics (waist/hip circumference)
- Blood draw (fasting)
- 36 (up to 46, if needed to ensure 36 paired biopsy samples) volunteer participants (18 HIV+/18 HIV-) will have a muscle biopsy
  - If muscle biopsy at the end of the study cannot be done (patient refuses, change in medications, etc), then the number of biopsies will increase to a maximum of 46 in order to ensure each group has at least 18 paired (entry/completion) biopsy samples.
- Questionnaires

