- Between the procedure #1 visit and the first exercise visit, participants will be sent home with an ActiWatch Spectrum monitor for activity and sleep.
- Between consent/baseline visit and procedure visit #1, patients will be sent home with a specimen cup with biosafety bag to collect stool and a 3 day dietary log. The log should be collected in real time during a 3 day time period preceding the procedure visit.
- Participants will be asked to collect stool within 72h period (if possible) prior to procedure visit #1 and place sample in a biosafety bag in their home freezer. They will bring the sample to procedure visit and it will be placed immediately in a -80C freezer within the RC2 11th floor lab.

**3. Exercise training.** The exercise intervention will begin at least 24 hours following, and within 14 days of the procedure visit (+/- 14 days for illness, scheduled vacation, etc).

- At the first visit, all participants will repeat physical function testing & 1-RM
- The first 2 weeks will be a lead-in period with low intensity exercise to gain familiarity with the machines. He/she will then be advanced to a moderate intensity exercise for an additional 10 weeks.
- During the exercise training, participants will come to the research center 3 to 4 days/week.
- Chair rise will be measured at the first visit of the week, every 2 weeks and pedometer data will be downloaded.
- To account for unforeseen absences from exercise (due to death of family/friends, illness, etc), the duration of exercise can be extended by up to 4 weeks. This will allow the participant to slowly acclimate back to the prior exercise intensity and minimize risk for injury. The exercise will only be extended if the participant is in agreement. If he/she wishes to complete the exercise intervention within the 24 weeks as planned, then the duration will not be extended.

4. **Acute inflammation visit 1.** At 3 time points during the study, participants will have an “acute exercise visit”.
  - The first will occur during week two of exercise
  - Participants will be asked to exercise on Monday, Thursday, and Friday.
  - **Thursday (beginning between 7:30-10am)** will consist of a high intensity CV + REx exercise stimulus, and a blood draw prior to exercise, and 0, 60, and 90 minutes following an exercise stimulus.

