  - Participants will be encouraged to avoid a large meal before exercise (snack is ok and encouraged). Blood pressure will be monitored before exercise, after the CVEx, and after the REx. As the expected response to exercise would be an increase in blood pressure, the PI will be contacted for any decreases in blood pressure after exercise.
5. **Week 12.**
  - Full physical function, anthropomorphics, questionnaires will be administered on Monday of week 12
  - The **Acute Inflammation visit 2** will occur on Thursday morning of week 12 (**beginning between 7:30-10am**). Arrangements for alternative dates can be made, but the participant must have at least 48 hrs from the prior exercise session). Participants will be encouraged to avoid a large meal before exercise (snack is ok and encouraged). Blood pressure will be monitored before exercise, after the CVEx, and after the REx. As the expected response to exercise would be an increase in blood pressure, the PI will be contacted for any decreases in blood pressure after exercise.
6. **Randomization/Week 13 visit.** At week 13, participants remaining on study will be randomized to either continue moderate intensity or advance to a higher-intensity exercise regimen with the randomization sequence generated by the study statistician ([name]).
  - V02, 1-RM will be measured on Monday of this week to develop a new prescription.
7. **Week 23.**
  - V02, 1-RM will be measured between Wed-Friday of this week.
8. **Week 24.**
  - **Acute inflammation visit 3.** During the week 24 of exercise, participants will be asked to exercise on Monday, Thursday, and Friday.
  - **Thursday (between 7:30-10 am)** will consist of a high intensity CV + REx exercise stimulus, and a blood draw prior to, and 0, 60, and 90 minutes following an exercise stimulus. Participants will be encouraged to avoid a large meal before exercise (snack is ok and encouraged). Blood pressure will be monitored before exercise, after the CVEx, and after the REx. As the expected response to exercise would be an increase in blood pressure, the PI will be contacted for any decreases in blood pressure after exercise.
  - Full physical function testing will occur on the final day of the exercise intervention
9. **Procedure visit #2.** Participants will return >48 hours after the last exercise session for a 2nd procedure visit for muscle biopsy (n=36), DXA scan, and blood draw.
  - DXA
  - Fasting for muscle biopsy (n=36)

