Outcome measures will be available bi-weekly for chair rise, and three times for other functional measures. Serum IGF-I, IGFBP3, muscle IGF-1 mRNA/protein, visceral fat, LBM, and inflammatory cytokines will be measured at procedure visits #1 and #2. Secondary outcomes will include change in other cytokines and hormones, sleep quality, quality of life, V02 peak, strength, and modified SPPB. The inflammatory markers will be tested as mediators on the effect of exercise on changes in function and LBM. Additional secondary outcomes will determine if sedentary time increases as the physical activity intensity decreases, the impact of the intervention on the affect and efficacy of exercise. These factors will be important in design of larger interventions and dissemination to identify points of low exercise efficacy and poor affect and attempt to prevent drop-outs from the intervention. An important outcome is to ensure that intensive 3x/week physical activity does not lead to a decrease in usual activity and an increase in sedentary time due to exercise-related fatigue.

For the inflammatory analyses:

**Analysis.** We propose that no subjects in either arm will experience a major injury (e.g., muscle strain or other injury requiring self-prescribed or provider prescribed treatment) and no more than 1 subject in each group will drop out because of exercise-induced discomfort

(i.e., fatigue, muscle or joint pain). The step counts between arms will be compared to determine if the high-intensity group limits non-study activity. For Aim 3, we will compare the change between arms in IL-6, TNF $\alpha$  and sTNFRI (pre-exercise, and 0, 60, and 90 minutes, and 24 hours) with a single bout of exercise at weeks 2, 12, and 24. We also will compare relative changes in serum IL-6, TNF $\alpha$  and sTNFRI from week 2 to week 24 between groups using geometric means and 95% confidence intervals. Secondary outcomes will include the change in other inflammation (sTNFRII, hsCRP, IL-10) and immune activation (sCD14, sCD163) markers, change in physical function, QoL, depressive symptoms, and exercise self-efficacy between study arms. **Sample size and power.** Sample size calculations were conducted for the within and between group percent change in IL-6, TNF $\alpha$ , hs-CRP, and sTNFRI levels. Data from 49 HIV+ subjects with higher function were used to estimate sample size parameters. We anticipate additional power using

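### Aim 3 plans arm comparisons of the acute inflammatory response at two visits before intensity is randomised, and states no acute HIV+ v HIV- test for Hypothesis 3a

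*Combined protocol and SAP*

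**What the plan says.** **Analysis.** In the Data Analysis Plan (IV.F), the paragraph for the inflammatory analyses states: "For Aim 3, we will compare the change between arms in IL-6", with TNF-alpha and sTNFRI, "with a single bout of exercise at weeks 2, 12, and 24". It then compares week 2 to week 24 changes between groups, without saying which groups. The power text that follows anticipates an AUC summary.

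**Randomisation.** Section IV.C has all participants on a low-intensity lead-in and then moderate exercise through week 12. "Randomization to continue on moderate versus advance to high intensity will occur at week 13". Item 6 of that section adds who is allocated: "participants remaining on study will be randomized to either continue moderate intensity or advance to a higher-intensity exercise regimen".

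**Acute visits.** Of the three acute exercise visits, "The first will occur during week two of exercise" and the second "will occur on Thursday morning of week 12". The third is in week 24.

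**Hypotheses.** Under Specific Aim 3 (Section I), Hypothesis 3a reads "Older HIV+ adults will have a lower acute response to exercise", relative to HIV- adults, at baseline and after 12 weeks of training. Two hypotheses carry the label 3b. The first, on the acute response, compares high with moderate intensity in older HIV+ adults after 12 weeks of high-intensity training.

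**The concern.** A comparison of randomised groups is informative only once the groups have been treated differently. At weeks 2 and 12 nobody has yet been allocated, so any difference between the future intensity groups is chance.

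Those same two visits are the ones Hypothesis 3a needs, and it needs them split by HIV status. As written, the plan attaches an uninformative contrast to them and leaves the HIV contrast unstated. There is also a loss of data: a participant who leaves before week 13 can contribute to Hypothesis 3a but has no arm, so an arm-based analysis would drop that person.

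A smaller point concerns efficiency. The week-12 acute response is measured just before allocation, with the same kind of bout and sampling schedule as week 24, yet the plan does not name it as a covariate for the week-24 comparison.

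**Working it through.** **1. Visits against the randomisation date**

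| Acute visit | Relative to allocation (week 13) | Can show an intensity effect? | Hypothesis it serves |
|---|---|---|---|
| Week 2 | 11 weeks before | No | 3a (earliest acute visit) |
| Week 12 | 1 week before | No | 3a |
| Week 24 | 11 weeks after | Yes | Acute 3b |

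**2. What *arms* means.** The term is never defined. Evidence for intensity groups:
- The sentence just before the Aim 3 sentence compares step counts between arms to see whether the high-intensity group limits other activity.
- Table 3 is sized at 13 per group with parameters from 49 HIV+ subjects. The design has 18 HIV+ participants per intensity group. With the roughly 20% dropout assumed for the primary outcome, 18 x 0.8 = 14.4, close to 13. The HIV groups are 36 each, or 29 after dropout.

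Evidence for HIV groups: the Matching and Randomization text once calls the HIV- cohort an arm.

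**3. The plan's own figures.** Table 3's between-group figures reproduce with a noncentral-t, two-sample calculation on the log scale (13 per group, two-sided 0.05, 80% power). For IL-6 (log SD 0.629) the detectable increase/decrease is 105.5%/51.3%, against the stated 110%/52%. For TNF-alpha it is 36.9%/26.9% against 37%/28%, and for sTNFRI 33.2%/24.9% against 34%/25%. These figures are not in dispute. They matter here only as evidence on which groups were sized.

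**4. True-null comparisons.** Assume one summary per marker per visit (such as the AUC), each tested at 0.05.
- Total: 3 markers x 3 visits = 9 arm comparisons.
- Before randomisation: 3 markers x 2 visits = 6, all with a true difference of zero.
- Expected false positives: 6 x 0.05 = 0.3.
- Chance of at least one, if independent: 1 - 0.95^6 = 0.265, about 26%. Markers and visits are correlated within a person, so this is an upper guide.

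**5. Value of week-12 adjustment at week 24.** Against an unadjusted comparison, residual variance is multiplied by 1 - r², where r is the correlation between the week-12 and week-24 acute responses. The documents give no such r. The 0.7 under Table 3 is for paired measurements in a table of marker levels, so a range is shown.

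| r | 1 - r² | Reduction in variance |
|---|---|---|
| 0.3 | 0.91 | 9% |
| 0.5 | 0.75 | 25% |
| 0.7 | 0.51 | 49% |

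If the week-2 response were already in the model and all pairwise correlations were 0.7, adding week 12 would take residual variance from 0.51 to 1 - 2(0.49)/1.7 = 0.424. The reduction is then (0.51 - 0.424)/0.51, about 17%.

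**The case against.** **Arms could mean HIV groups.** If so, Hypothesis 3a is covered at weeks 2 and 12. This cannot be excluded, but it moves the gap rather than closing it: the acute Hypothesis 3b would then have no stated analysis. Under either reading one acute hypothesis lacks a test.

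**HIV comparisons appear elsewhere.** The general Analysis Plan evaluates groups by HIV status (or intensity), and the venipuncture section (IV.D, item 5) justifies blood sampling by the HIV+ v HIV- response in inflammation markers. So it would be wrong to infer that the plan never intends an HIV comparison of these markers. However, the general model is for change from week 0, when no acute bout takes place, and the venipuncture text states a purpose without a test. Neither specifies an acute comparison at weeks 2 and 12.

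**The sentence need not mean three separate tests.** A repeated-measures model could use weeks 2 and 12 as pre-randomisation values, which would be a sound use of them and would create no extra tests. The plan does not say this; it lists them as comparison visits. The count of 6 is therefore a maximum under visit-by-visit testing.

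**A larger count is tempting.** A reader might multiply 3 markers by 4 post-exercise samples by 2 visits to get 24 true nulls and a 71% chance of a false positive. The documents do not support that. No test at each sampling time is specified, an AUC is anticipated, and serial samples from the same people are far from independent.

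**Conclusion.** The point holds and should be corrected. On the most natural reading of *arms*, two of the three visits in the Aim 3 acute comparison cannot show an intensity effect, and Hypothesis 3a has no stated acute HIV+ v HIV- test. The conclusion rests on the plan's dates and on that reading of an undefined term; under the other reading the missing test is that of the acute Hypothesis 3b.

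The false-positive cost is modest: at most 6 true-null comparisons and 0.3 expected false positives, if each is tested at 0.05. The larger cost is that the stated test is aimed at the wrong contrast for Hypothesis 3a.

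Three further inferences go too far. The week-24 arm comparison is valid and is the right one for the acute Hypothesis 3b. A 49% gain in precision from week-12 adjustment cannot be claimed, because it borrows a correlation given for something else and presumes no baseline value is already in the model. Nor does this touch the primary outcome, which is chair rise.

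**What to change.** In the inflammatory analysis paragraph:

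1. Define *arms* as the randomised intensity groups, and say which groups the week 2 to week 24 comparison uses.
2. For Hypothesis 3a, compare the acute response (for example the AUC) between HIV+ and HIV- at week 2 and week 12. State that week 2 stands in for baseline as the earliest acute visit, and include participants who leave before week 13.
3. For the acute Hypothesis 3b, compare high with moderate intensity at week 24 among randomised HIV+ participants, with each participant's own week-12 acute response as a covariate. If HIV- participants are included, add an arm-by-HIV term, since that hypothesis concerns HIV+ adults.
4. Present any arm contrast at weeks 2 and 12 as a descriptive balance check, without a test of effect.

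The cost is a few sentences in the analysis plan. All the measurements are already scheduled.

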Table 3. Detectable % change from geometric mean needed to achieve 80% power

Outcome	Geometric Mean	Mean (SD) log scale	Within Group Change*		Between Groups Change	
			Increase	Decrease	Increase	Decrease
IL-6 (pg/mL)	0.98	-0.025 (0.629)	52%	34%	110%	52%
TNF $\alpha$ (pg/mL)	1.48	0.392 (0.274)	20%	17%	37%	28%
hs-CRP (mg/L)	1.55	0.440 (1.21)	120%	55%	300%	75%
sTNFRI (pg/mL)	997.9	6.91 (0.25)	24%	19%	34%	25%

\*standard deviation (SD) adjusted based on a 0.7 correlation between paired measurements.

the summary measure AUC. Table 3 contains the within and between group detectable percent change from the geometric mean was calculated assuming a sample size of 13 subjects per group, 80% power, a significance level of 0.05 and a two-sided two-sample t-test.

For the qualitative interviews:

Data Analysis: We will analyze transcribed interviews using a mixed inductive and deductive approach. To develop the codebook, a qualitative analyst and the PI will code a subset of interviews separately using ATLAS.ti software. Coding differences will be adjudicated by [name] (Co-I). The analyst will then code the remainder of the interviews. After open coding, key meanings and insights will be identified and then reduced to identify patterns. Themes will be explored and tested using iterative techniques across subsequent individual and group level interviews.

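### The week-24 acute cytokine response is to be compared between intensity arms with no stated use of each participant's two pre-randomisation bouts; adjusting for them is nearly free, but the power gain depends on a correlation the plan does not give

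*Combined protocol and SAP*

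**What the plan says.** Section C (Study Design and Research Methods) fixes the order of events. On the acute visits it states "The first will occur during week two of exercise"; the second is in week 12 and the third in week 24. On allocation it states "Randomization to continue on moderate versus advance to high intensity will occur at week 13". The Venipuncture section describes the same kind of high-intensity stimulus and the same markers at all three visits.

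The acute part of Hypothesis 3b (Specific Aim 3) concerns older HIV+ adults after 12 weeks on the high-intensity regimen. It predicts a larger IL-6 rise after a bout than on moderate intensity, "without a detrimental increase in TNF"-alpha.

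The inflammatory paragraph of section F (Data Analysis Plan) compares the change between arms in IL-6, TNF-alpha and sTNFRI "with a single bout of exercise at weeks 2, 12, and 24". It names no model and no covariate. A separate sentence covers relative change in serum levels "from week 2 to week 24 between groups using geometric means and 95% confidence intervals". An AUC is mentioned as a source of extra power but is not defined. Table 3 was computed "assuming a sample size of 13 subjects per group, 80% power, a significance level of 0.05 and a two-sided two-sample t-test". Its footnote, "standard deviation (SD) adjusted based on a 0.7 correlation between paired measurements", is attached to the within-group columns.

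The general Analysis Plan paragraph has a linear mixed model that includes the baseline value, but its outcome is change from week 0.

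**The concern.** Before week 13 everyone follows the same programme. A comparison of intensity arms on the acute response at week 2 or week 12 can therefore show only chance imbalance. Those two visits have a use in the serostatus comparison of Hypothesis 3a. For the intensity question their value is as baseline: each participant has two earlier measurements of the outcome compared at week 24, both taken before allocation, so neither can be affected by it.

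If they are left out, any stable difference between people in how strongly cytokines respond to a bout stays in the error term. With 13 per group, only large effects are detectable, and a covariate already collected is the cheapest way to reduce that error. Leaving the model open also means that the choice between raw response, change score and adjusted response, across three markers, could be made after the data are seen.

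**Working it through.** **Inputs.** From the Table 3 text: 13 per group, two-sided alpha 0.05, 80% power, two-sample t-test. From Table 3: log-scale SDs of 0.629 (IL-6), 0.274 (TNF-alpha), 1.21 (hs-CRP) and 0.25 (sTNFRI). Assumed, because the documents give no value: the correlation ρ of the acute response between visits, taken as equal for all pairs of visits and varied from 0 to 0.7.

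**Step 1: reproduce Table 3.** With 24 degrees of freedom and noncentrality d·√(13/2), 80% power needs d = 1.145. The detectable increase is exp(d·SD) − 1 and the detectable decrease is 1 − exp(−d·SD).

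| Marker | Recomputed increase / decrease | Stated |
|---|---|---|
| IL-6 | 106% / 51% | 110% / 52% |
| TNF-alpha | 37% / 27% | 37% / 28% |
| hs-CRP | 300% / 75% | 300% / 75% |
| sTNFRI | 33% / 25% | 34% / 25% |

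Apart from apparent rounding up, the between-group columns follow from the unadjusted SDs. No within-person information enters them.

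**Step 2: add the earlier responses.** ANCOVA multiplies the residual variance by 1 − R².

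- Week 12 only: R² = ρ².
- Mean of weeks 2 and 12: R² = ρ² / ((1 + ρ)/2) = 2ρ²/(1 + ρ).

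The effect becomes 1.145/√(1 − R²), tested on 24 − 1 = 23 degrees of freedom. For example, at ρ = 0.5 with the mean of both, R² = 0.5/1.5 = 0.333 and the effect is 1.145/√0.667 = 1.40, which gives 93% power.

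| ρ | R², week 12 / mean of both | Power, week 12 only | Power, mean of both |
|---|---|---|---|
| 0 | 0 / 0 | 79.8% | 79.8% |
| 0.3 | 0.09 / 0.138 | 83.4% | 85.4% |
| 0.4 | 0.16 / 0.229 | 86.2% | 88.9% |
| 0.5 | 0.25 / 0.333 | 89.8% | 92.8% |
| 0.7 | 0.49 / 0.576 | 97.5% | 99.0% |

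A gain of 10 points needs ρ of about 0.51 with week 12 only, or 0.43 with the mean of both.

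**Step 3: what could reduce the gain.** One further degree of freedom for gender changes these figures by less than 0.2 points. Allowing for average chance imbalance in the covariate (residual variance times 1 + 1/22) gives, with the mean of both, 78.1%, 83.8%, 91.7% and 98.7% at ρ = 0, 0.3, 0.5 and 0.7. The worst case is then a loss of about 2 points.

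**Step 4: is ρ = 0 realistic?** The only correlation in the plan, 0.7, is for paired marker levels. The acute outcome is a change within a bout. If all levels, pre and post and at any visit, had equal variance and correlated at 0.7, the covariance of two visits' changes would be proportional to 0.7 − 0.7 − 0.7 + 0.7 = 0. The plan's own figure is thus compatible with no gain, and ρ = 0 belongs in the range.

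**The case against.** The strongest reply is that the plan is silent on adjustment and does not reject it. The t-test appears as a sample-size assumption, and the general mixed model includes a baseline value. This stands in part: a reader might infer that an unadjusted analysis has been chosen, and the documents do not say so. The mixed model does not close the gap, however. Its outcome is change from week 0, when no acute bout is done, and the inflammatory analyses are set out separately with no reference to it. The week-2 to week-24 sentence does not close it either, because it concerns serum levels. Even if the acute endpoint were a change score from one earlier visit with 80% power, adjusting for week 12 or for the mean of both would give 86% or 91% at ρ = 0.7, and 90% or 93% at ρ = 0.5.

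A second reply is that this is not the trial's primary outcome, which is chair rise, and that randomisation already protects an unadjusted comparison from systematic bias. Both are correct. The point is about efficiency and pre-specification; it is not a flaw in validity.

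A reader might also infer that the AUC confounds resting level with acute response. That is not shown. The AUC is never defined and could be incremental.

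**Conclusion.** The point holds as a gap in the analysis plan. Two pre-randomisation measurements of the week-24 acute response exist, and no between-arm analysis of that response is said to use them. The size is conditional: from 80% power at 13 per group, roughly no change at ρ = 0 (under 1 point lost to degrees of freedom, about 2 with chance imbalance), 3 to 5 points gained at 0.3, 10 to 13 at 0.5 and 17 to 19 at 0.7.

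It is tempting to carry the plan's 0.7 over and claim a loss of 10 or more points. The documents do not support that, because 0.7 describes paired levels and no correlation is given for acute responses. The figures also assume equal correlation among the three visits. They are in SD units, because Table 3's SDs describe marker levels in HIV+ subjects and not responses to a bout.

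**What to change.** Name the week-24 visit as the randomised between-arm test of the acute response. Analyse the log-scale response, defined as change from that bout's pre-exercise value or as an incremental AUC with its sampling times stated, by ANCOVA. Include as covariates the participant's mean response at weeks 2 and 12, computed the same way, and gender, which is the blocking factor in the randomisation. Add HIV status only if both serostatus groups are pooled; in the HIV+ contrast of Hypothesis 3b it is constant.

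Do not add the week-24 pre-exercise level as a covariate. It is measured after randomisation, and Aim 3 expects high-intensity training to lower resting markers by then, so conditioning on it would compromise the randomised contrast. Taking the response as a change or an incremental area already accounts for the starting level of the bout.

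State the expected power as a range over ρ. The change is wording only: it needs no new samples and no change to visits, and costs two degrees of freedom, or three if serostatus groups are pooled.
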